6.5.1. Interim Analysis

There is one planned IA at 75% of total target cases across the 2 treatment groups and a final analysis for the first null hypothesis to be tested to support the primary objective. The main intent of the IA is for early detection of reliable evidence that rVE of mRNA-1010 is noninferior to the active comparator. The Lan-DeMets Pocock approximation spending function is used for calculating efficacy boundaries and to preserve the (one-sided) 2.5% Type I error rate over the IAs and the final analysis (when the target number of cases have been observed).

The NI hypotheses are as follows:

Null hypothesis: $H_0^1: rVE \leq -10\%$ (inferior)

Alternative hypothesis: $H_a^1: rVE > -10\%$ (non-inferior)

Equivalently, the NI hypotheses are:

$H_0^1: HR \geq 1.1$ (inferior)

$H_a^1: HR < 1.1$ (non-inferior)

If NI is demonstrated at an IA, the subsequent analyses will be considered supportive in nature for the NI claim. The DSMB will review the IA results and make recommendations to the Sponsor in terms of study results reporting and unblinding based on the boundaries of early efficacy as described in this section, safety data, and data external to this study.

[Table 5](#) summarizes the timing, number of cases, and decision guidance at each IA and final analysis.

Table 5: Interim Boundaries Using Lan-DeMets Pocock Spending Function, Calculation Based on the PP Set for the Endpoint Supporting the Primary Objective

| Information Fraction (% of total #cases) | Number of Cases | Nominal Alpha (1-sided) \pm | Efficacy Boundary Rejecting H_0 : $rVE \leq -10\%$ | Cumulative Probability (Crossing Efficacy Boundary if the True $rVE = 25\%$) |
|--|-----------------|-------------------------------|--|---|
| IA (75%) | 274 | 2.07% | $rVE \geq 14.0\%$ ($HR \leq 0.860$) | 78.9% |
| Final Analysis (100%) | 365 | 1.2% | $rVE \geq 13.2\%$ ($HR \leq 0.868$) | 95.0% |

\pm : a actual nominal alpha may be adjusted based on the actual information fraction at individual IA(s).

The IA will occur with data cut-off around the middle of February in 2023 when approximately 75% of the total cases in the PP Set are expected to be observed. The study will be considered positive (non-inferior) at IA if the one-sided p-value for rejecting $HR \geq 1.1$ is less than 2.07% based on the Lan-DeMets Pocock approximation spending function, provided that IA is conducted exactly at the 75% information fraction. The nominal alpha to be spent at the IA and final analysis may be adjusted according to the actual number of cases observed at IA.

If NI is demonstrated at IA, the superiority claim in the same primary endpoint will be evaluated to support the primary objective, i.e., H_0^2 : $HR \geq 1$ (equivalently, $rVE \leq 0\%$). Approximately 290 cases are expected to be observed in the mITT Set at IA. Superiority of mRNA-1010 relative to the active comparator is demonstrated if the one-sided p-value for rejecting $HR \geq 1$ (equivalently, $rVE \leq 0\%$) is less than 2.07% based on the Lan-DeMets Pocock approximation spending function. The nominal alpha to be spent at the IA and final analysis may be adjusted according to the actual number of cases observed at IA.

No formal statistical testing is planned at the IA for key secondary and other secondary efficacy endpoints. However, descriptive summarizations and statistical analyses may be conducted in an exploratory manner to support the primary endpoint.

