9.6. Planned Analyses

9.6.1. Interim Analyses

There is one planned IA with data cut-off around the middle of February 2023 regardless of number of influenza cases accrued for the first null hypothesis to be tested to support the primary objective. The intent of the IA is for early detection of reliable evidence that rVE of mRNA-1010 is noninferior to the active comparator. The Lan-DeMets Pocock boundaries are used for calculating efficacy boundaries and to preserve the (1-sided) 2.5% Type I error rate over the IA and the final analysis (when the target number of cases have been observed), relative to the hypothesis:

$$H_0^1: HR \geq 1.1 \text{ (equivalently, rVE} \leq -10\%).$$

If NI is demonstrated at an IA, the subsequent final analysis will be considered supportive in nature for the NI claim. The DSMB will review the IA results and make recommendations to the Sponsor in terms of study results reporting and unblinding based on the boundaries of early efficacy as described in this section.

Table 8 summarizes the timing, number of cases, and decision guidance at each IA and final analysis.

Table 8: Interim Boundaries Using Lan-DeMets Pocock Spending Function, Calculation Based on the PP Set for the Endpoint Supporting the Primary Objective

Information Fraction (% of total #cases)	Number of Cases	Nominal Alpha (1-sided) ±	Efficacy Boundary Rejecting H_0 : rVE \leq -10%	Cumulative Probability (Crossing Efficacy Boundary if the True rVE = 25%)
IA (75% cases assumed)	274	2.07%	rVE \geq 14.0% (HR \leq 0.860)	87.1%
Final Analysis (100%)	365	1.2%	rVE \geq 13.2% (HR \leq 0.868)	93.7%

Abbreviations: HR = hazard ratio; IA: interim analysis; PP = per-protocol; rVE = relative vaccine efficacy.
 ±: actual nominal alpha may be adjusted based on the actual information fraction at individual IA(s).

The study will be considered positive (rVE has been demonstrate) if the *p-value* for rejecting HR \geq 1.1 is less than 2.07% based on the Lan-DeMets Pocock alpha spending function, provided that the IA is conducted exactly at 75% information fraction. The final analysis will be performed when approximately 365 cases have been observed in the PP Set. In the case that the early study success is not achieved, the study will be considered positive at the final analysis if the 1-sided *p-value* for rejecting HR \leq 1.1 is less than 1.2%.

[figure not shown]

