In addition to the information presented in the statistical considerations section of the protocol (Section 9) which provides the principal features of analyses for this study, this SAP provides statistical analysis details and data derivations. It also documents modifications or additions to the analysis plan which are not “principal” in nature and result from information that was not available at the time of protocol finalization. If the methods in this SAP differ from the methods described in the protocol, the SAP will prevail.

Study mRNA-1010-P302 is a Phase 3, randomized, observer-blind, active-controlled study to evaluate the safety and efficacy of mRNA-1010 candidate seasonal influenza vaccine as compared with an active comparator in adults ≥ 50 years of age.

Parexel Biostatistics and programming team, designee of Moderna Biostatistics and Programming department, will perform the statistical analysis; Statistical Analysis System (SAS) Version 9.4 or higher will be used.

In this document, injection of investigational product (IP), injection, vaccination, and dose are used interchangeably; vaccination group and treatment group are used interchangeably.

2. Study Objectives

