4.3. Sample Size and Power

This Phase 3 study will plan to randomize approximately 23,000 participants in a 1:1 ratio to the mRNA-1010 or the active comparator groups. Therefore, approximately 11,500 participants will be randomized to each group.

The sample size is driven by the total number of cases to demonstrate rVE (mRNA-1010 vs. active comparator) to prevent the first episode of RT-PCR confirmed protocol-defined ILI caused by any influenza A or B virus strains.

Under the assumption of proportional hazards and with 1:1 randomization of mRNA-1010 and active comparator, a total of 365 cases in the PP Set will provide at least 93% power to establish a NI claim with a NIM = 10%, i.e., rejecting the null hypothesis $H_0^1: rVE \leq -10\%$,

with one IA using the Lan-DeMets Pocock boundary for efficacy and a log-rank test statistic with an overall one-sided Type I error rate of 2.5%.

The number of cases will be continuously monitored using external epidemiologic data (e.g., CDC.gov). It is projected that by middle of February 2023, approximately 274 cases (75% of the targeted cases) will be observed in the PP Set. In the scenario that fewer cases are observed by middle of February, the IA will still be conducted around this timeframe because of the seasonality of influenza in the Northern Hemisphere, and the nominal alpha to be spent at the IA and final analysis will be adjusted accordingly.

The total number of cases pertains to the PP Set accruing at least 14 days after study intervention. Approximately 23,000 participants will be randomized with the following assumptions:

- The target rVE of mRNA-1010 to the active comparator is 25% to prevent the first episode of RT-PCR confirmed protocol-defined ILI caused by any influenza A or B virus strains.
- An attack rate of 2% in the active comparator for the primary endpoint.
- One IA in the middle of February 2023 with approximately 75% of total target cases expected across 2 study intervention groups in the PP Set.
- A dropout rate ~ 10% (not evaluable for the PP Set).
- Type I error rate will be adjusted using the Lan-DeMets Pocock boundary.

If the IA is conducted exactly at 75% of total target cases, the nominal one-sided Type I error rate will be 2.07% at IA, and 1.2% at the final analysis for NI testing, respectively.

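### SAP Table 5 states noninferiority crossing probabilities of 78.9% and 95.0%, but its own boundaries give 87.1% and 93.7%

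*SAP*

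**What the plan says.** SAP Section 6.5.1 presents "Table 5: Interim Boundaries Using Lan-DeMets Pocock Spending Function, Calculation Based on the PP Set for the Endpoint Supporting the Primary Objective". The accompanying text says that the table "summarizes the timing, number of cases, and decision guidance at each IA and final analysis". Protocol Section 9.6.1 introduces its counterpart the same way: "Table 8 summarizes the timing, number of cases, and decision guidance at each IA and final analysis".

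The two tables agree in every column except the last:

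| | Cases | Nominal one-sided alpha | HR boundary | Crossing probability, Protocol Table 8 | Crossing probability, SAP Table 5 |
|---|---|---|---|---|---|
| IA (75%) | 274 | 2.07% | 0.860 | 87.1% | 78.9% |
| Final (100%) | 365 | 1.2% | 0.868 | 93.7% | 95.0% |

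Both last columns are headed as cumulative probabilities for a true rVE of 25%. SAP Section 4.3 adds that "a total of 365 cases in the PP Set will provide at least 93% power", "with one IA using the Lan-DeMets Pocock boundary for efficacy and a log-rank test statistic with an overall one-sided Type I error rate of 2.5" per cent. SAP Section 7 reports no changes from the analyses planned in the protocol.

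**The concern.** One design with one set of inputs cannot have two different pairs of crossing probabilities, so at least one table is wrong. The column gives the operating characteristics of the primary NI test: the chance of an early claim and the overall power. It stands in the section that sets out the boundaries for the DSMB's recommendation.

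The SAP's pair also hides the trade-off in the chosen design. Pocock-type spending raises the chance of success at the IA and costs some final power. The SAP column shows less of the gain and none of the cost. A reader who checks the column against the boundaries could reasonably doubt which spending function the table was built on.

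**Working it through.** **Inputs.** Cases 274 and 365, HR boundaries, nominal alphas and true rVE 25% (HR 0.75): SAP Table 5. Null HR 1.1: SAP Section 4.2.1. Overall one-sided alpha 2.5%, Lan-DeMets Pocock spending, log-rank statistic, 1:1 randomization: SAP Section 4.3.

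**Step 1: reproduce the alphas and boundaries.**

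- Information fraction: t = 274/365 = 0.7507.
- Alpha spent at the IA: 0.025 × ln(1 + (e − 1)t) = 0.0207, so z₁ = 2.039. The table's 2.07% is confirmed.
- Final critical value: solve P(Z₁ > 2.039 or Z₂ > z₂) = 0.025 under the null with correlation √t. This gives z₂ = 2.258, nominal alpha 1.196%. The table's 1.2% is confirmed.
- HR boundary: 1.1 × exp(−2z/√D). At 274 cases this is 0.860 and at 365 cases 0.868. Both are confirmed.

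**Step 2: crossing probabilities at HR 0.75.** The mean of the test statistic is ln(1.1/0.75) × √D/2, which is 3.170 at 274 cases and 3.659 at 365.

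- IA: Φ(3.170 − 2.039) = 87.1%.
- Cumulative: 1 − P(Z₁ ≤ 2.039 and Z₂ ≤ 2.258) from the bivariate normal with means 3.170 and 3.659 and correlation √t = 93.7%.

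These equal protocol Table 8. A shorter check of the IA row uses only the printed boundary: Φ(ln(0.860/0.75) × √274/2) = 87.1%.

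**Step 3: could another calculation explain the SAP pair?**

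| Calculation | IA | Cumulative |
|---|---|---|
| Pocock, variance D/4 (as above) | 87.1% | 93.7% |
| Pocock, event split under HR 0.75 | 86.4% | 93.2% |
| Pocock, event split under HR 1.1 | 87.0% | 93.6% |
| Pocock, Freedman formula | 86.3% | 93.1% |
| Simulation from the rounded HR boundaries | 86.6% | 93.4% |
| Lan-DeMets O'Brien-Fleming, variance D/4 | 79.7% | 95.2% |
| Lan-DeMets O'Brien-Fleming, event split under HR 0.75 | 78.8% | 94.9% |
| SAP Table 5 | 78.9% | 95.0% |

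No Pocock variant comes near 78.9% or reaches 95.0%. To obtain 78.9% at 274 cases, the nominal alpha at the IA would have to be about 0.90%, less than half the 2.07% printed in the same row. O'Brien-Fleming spending does land close to the SAP pair, but its HR boundaries would be about 0.829 and 0.891, not the ones in the table. The protocol's summary of changes records a move from O'Brien-Fleming to Pocock in Amendment 1, so the column may have been carried over from the previous design. That is an inference; the documents do not say so, and the error does not depend on it.

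**The case against.** The strongest reply is that nothing in the trial turns on this column. NI success is decided by the one-sided p-value against the nominal alpha, and the cases, alphas and boundaries are right. The probabilities enter no test, stopping rule, sample size or error-rate calculation. The power of at least 93% in SAP Section 4.3 remains true at 93.7%, and the final entry is off by only 1.3 points. The IA takes place around mid-February 2023 whatever the case count, so either IA figure applies only if the information fraction is close to 75%.

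All of this stands, and it limits the consequence. The SAP's precedence rule, "If the methods in this SAP differ from the methods described in the protocol, the SAP will prevail", does not add weight either: it concerns methods, and the methods here are the same in both documents. What the reply does not do is make the figures right. The arithmetic is not in dispute, and an 8.2-point gap at the IA is too large for rounding or the choice of variance formula.

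**Conclusion.** The concern holds. On the table's own inputs, the last column of SAP Table 5 is wrong in both rows:

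- IA: 78.9% stated, 87.1% computed; 87.1 − 78.9 = 8.2 points too low.
- Cumulative at the final analysis: 95.0% stated, 93.7% computed; 95.0 − 93.7 = 1.3 points too high. The chance of missing NI at the target rVE is 100 − 93.7 = 6.3%, not 5.0%.

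The IA entry is the clear numerical error. The final entry is a smaller discrepancy, but it conflicts with protocol Table 8 on identical inputs.

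The result assumes proportional hazards, a true HR of 0.75, 1:1 allocation and an IA at exactly 274 of 365 cases, as both tables do. Across the Pocock calculations tried, the range is about 86% to 87% at the IA and 93.1% to 93.7% cumulatively. The error is confined to the stated operating characteristics; Type I error control and the decision rule are sound.

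**What to change.** In SAP Table 5, replace 78.9% with 87.1% and 95.0% with 93.7%. Leave the case numbers, nominal alphas and HR boundaries as they are. This restores agreement with protocol Table 8 and with the table's own boundaries. The cost is two numbers in one table, and the stated final power becomes slightly less favourable. No analysis, sample size or boundary changes.

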6.5.2. Final Analysis

If the primary NI objective is not achieved at IA, it will be evaluated again at the final analysis, when approximately 365 cases have been observed in the PP Set. The study will be considered positive (non-inferior) at the final analysis if the one-sided p-value for rejecting $HR \geq 1.1$ is less than 1.2% based on the Lan-DeMets Pocock approximation spending function.

Similarly, if the primary superiority objective is not achieved at IA, it will be evaluated again using the same primary endpoint at the final analysis, provided that the NI has been demonstrated (either at the IA or at the final analysis). Approximately 386 cases are expected to have been observed in the mITT Set. Superiority of mRNA-1010 relative to the active comparator is demonstrated if the one-sided p-value for rejecting $HR \geq 1$ is less than 1.2% based on the Lan-DeMets Pocock approximation spending function.

Note that the actual nominal alpha may be adjusted based on the actual information fraction at individual IA.

Following the multiplicity adjustment procedure described in [Section 6.6](#), the NI and superiority testing for the key secondary efficacy endpoints will be performed at the final analysis. Upon successes achieved for the preceding analyses pre-specified in the hierarchical testing sequence ([Figure 1](#)), the NI and superiority in the key secondary efficacy endpoints will be demonstrated if the one-sided p-value for each of the hypothesis testing is less than 2.5%.

Analyses of other secondary efficacy endpoints may be conducted to support the primary and key secondary efficacy endpoints. No formal statistical testing is planned for these analyses.

6.5.3. End-of-Study Analysis

[figure not shown]
An EoS analysis may be performed at the end of the study when all study participants have completed the final visit on Day 361 (Month 12) or have withdrawn from the study. The study database will be cleaned and locked, and the study will be unblinded. The final analysis and the EoS analysis may be combined if timing allows.

Analyses for the primary, key secondary, and other secondary efficacy endpoints may be re-run as supportive analyses.

6.6. Multiplicity Adjustment

To control the overall one-sided Type I error rate for the study, a hierarchical testing strategy will be used to test the primary and secondary efficacy endpoints ([Figure 1](#)).

Figure 1: Testing Sequence of the Primary and Secondary Endpoints

Noninferiority of mRNA-1010 vs. the active comparator on the primary efficacy endpoint will be declared if the one-sided p-value for rejecting $HR \geq 1.1$ is less than the nominal alpha based on the Lan-DeMets Pocock approximation spending function, based on the PP Set. The nominal alpha levels (one-sided) are 2.07%, and 1.2% at the IA and final analysis,

respectively, if the IA is conducted when 75% of total target cases are accumulated across the 2 groups.

If the NI criteria is met for the primary efficacy endpoint, superiority of mRNA-1010 relative to the active comparator will be tested on the mITT Set. The superiority of rVE will be demonstrated if the one-sided p-value for rejecting $HR \geq 1$ is less than the nominal alpha based on the Lan-DeMets Pocock approximation spending function, based on the mITT Set. For this superiority testing, the nominal one-sided alpha level will be 2.07% and 1.2% at the planned IA and final analysis, respectively, if the IA is conducted when 75% of total target cases are accumulated across the two treatment groups.

If the above superiority is demonstrated, then the following secondary efficacy endpoints will be evaluated for NI and superiority in the order outlined in [Figure 1](#) at the final analysis using a one-sided 2.5% Type I error rate:

- rVE of mRNA-1010 vs. the active comparator against the first episode of RT-PCR confirmed protocol-defined ILI caused by influenza A or B virus strains with similarity to the seasonal influenza vaccine strains.
- rVE of mRNA-1010 vs. the active comparator against the first episode of RT-PCR confirmed protocol-defined ILI caused by influenza A or B virus strains antigenically matched to the seasonal influenza vaccine strains.

The testing sequence can only continue to the next level if all tests at the higher level achieve statistical significance at the 2.5% alpha level. If a test at the higher level fails to demonstrate statistical significance, then the testing sequence will stop, and all testing thereafter will not be conducted.

Analyses of other remaining secondary efficacy endpoints are not controlled for multiplicity.

6.7. Safety Analysis

Safety and reactogenicity will be assessed by clinical review of all relevant parameters including solicited ARs (local and systemic), unsolicited AEs, SAEs, MAAEs, AESIs, AEs leading to withdrawal from study participation, vital signs, and physical examination

findings. Solicited ARs and unsolicited AEs will be coded by SOC and PT according to the MedDRA version 25.0. All safety endpoints will be summarized by vaccination group corresponding to the actual IP they received for the Safety Set, except summaries of solicited ARs, which will be based on the Solicited Safety Set.

When summarizing the number and percentage of participants with an event, participants with multiple occurrences of the same AE/AR or a continuing AE/AR will be counted once. AE/AR data will be summarized according to the highest severity/toxicity in the summaries by severity/toxicity, if participants reported multiple events under the same SOC and/or PT. SOC will be displayed in internationally agreed order. PT will be displayed in descending order of frequency of mRNA-1010 vaccination group within each SOC.

6.7.1. Solicited Adverse Reactions

Solicited ARs are a subset of AEs in which there is a reasonable possibility that the IP caused the AE. These AEs consist of selected signs and symptoms that participants are asked to record/report. In this study, the solicited ARs are reactogenicity events. The term “reactogenicity” refers to the occurrence of transient adverse effects associated with vaccine administration.

The solicited ARs are recorded by the participant in the eDiary. The eDiary will solicit daily participant reporting of occurrence and intensity of ARs using a structured checklist from Day 1 through Day 7 after the IP injection (i.e., the day of injection and 6 subsequent days). If any solicited ARs reported during the 7-day follow-up post injection are not captured in the eDiary, then they should be reported in the Reactogenicity eCRF.

Solicited ARs reported in both the eCRF and eDiary will be included in the evaluation of solicited ARs.

If an event starts during the solicited period (i.e., from Day 1 through Day 7 after the IP injection), but continues beyond 7 days after dosing, the participants should notify the site to provide an end date and close out the event on the Reactogenicity page of the eCRF.

If a solicited local or systemic AR starts on or after Day 8, it should be captured on the AE eCRF page until no longer reported.

Any solicited AR that meets any of the following criteria must be entered into the participant's source document and must be recorded in the participant's Reactogenicity eCRF:

- Solicited local or systemic AR that results in a visit to a healthcare practitioner
- Solicited local or systemic AR leading to the participant withdrawing from the study or the participant being withdrawn from the study by the investigator (AE leading to withdrawal)
- Solicited local or systemic AR continuing beyond 7 days post injection
- Solicited local or systemic AR that otherwise meets the definition of an SAE

The following local ARs will be recorded daily by the participants in the eDiary:

- Injection site pain
- Injection site erythema (redness)
- Injection site swelling/induration (hardness)
- Axillary (underarm) swelling or tenderness ipsilateral to the side of injection

The following systemic ARs will be recorded daily by the participants in the eDiary:

- Headache
- Fatigue
- Myalgia (muscle aches all over the body)
- Arthralgia (aches in several joints)
- Nausea/vomiting
- Chills
- Fever (an oral temperature greater than or equal to 38.0°C/100.4°F)

The solicited ARs will be graded based on the grading scales presented in [Appendix E](#), modified from the Toxicity Grading Scale for Healthy Adult and Adolescent Volunteers Enrolled in Preventative Vaccine Clinical Trials ([DHHS 2007](#)).

All solicited ARs (local and systemic) will be considered causally related to dosing.

Analyses of solicited ARs will be provided by vaccination group based on the Solicited Safety Set, unless otherwise specified.

The number and percentage of participants with any solicited local ARs, solicited systemic ARs, and any solicited ARs during the 7-day follow-up period after vaccination will be summarized, along with the number of events under each category. A two-sided 95% exact CI using the Clopper-Pearson method will be provided for the percentage of participants who reported any solicited local AR, solicited systemic AR, or any solicited AR.

The number and percentage of participants who reported each individual solicited local AR (with a toxicity grade of Grade 1 or greater) and solicited systemic AR (with a toxicity grade of Grade 1 or greater) during the 7-day follow-up period after vaccination will be provided by toxicity grade.

The onset of individual solicited AR is defined as the time point after injection at which the respective solicited AR first occurred. The number and percentage of participants with onset of individual solicited ARs will be summarized by study day relative to the injection (Day 1 through Day 7).

Descriptive statistics will be provided for the duration of solicited ARs (overall, local, and systemic) and each individual solicited AR by vaccination group. The duration of local or systemic solicited ARs, along with the specific individual solicited ARs, will be calculated as: reaction end date – reaction start date + 1, regardless of whether it is intermittent, continued, or continued beyond 7 days.

Separate bar charts will be provided for the summary of local and systemic solicited adverse reactions within 7 days after vaccination

All solicited ARs that continue beyond 7 days post-injection will be summarized.

All delayed ARs with first onset day after 7 days post-injection will also be summarized.

The above analyses of solicited ARs will be provided for the following subgroups ([Table 2](#)):

- Age group 1: ≥ 50 to < 65 years or ≥ 65 years
- Age group 2: ≥ 50 to < 65 years, ≥ 65 to < 75 years, or ≥ 75 years
- Sex: Female or Male
- Race: White, Black or African American, Asian, or Other

These summaries may be provided for additional subgroups of selected baseline characteristics.

